1. INTRODUCTION

1.1 Abstract

Bacterial vaginosis (BV) is the most common cause of vaginal discharge among reproductive aged women in the United States. It has an estimated prevalence of 30% or nearly 1 in 3 reproductive aged women. BV is an established risk factor for adverse outcomes in pregnancy, including preterm labor, preterm premature rupture of membranes, and chorioamnionitis, all of which increase the risk of postpartum complications including endometritis and surgical site infections (SSI). Infants born to women with BV have higher incidence of neonatal sepsis, respiratory distress, Neonatal Intensive Care Unit (NICU) admissions and low birth weight, as well as long-term adverse outcomes, irrespective of maternal peripartum infection. Prior studies have demonstrated that treating pregnant women with BV potentially reduces the risk of preterm labor. However, no studies have evaluated the impact of treating BV on the incidence of maternal peripartum infections, including chorioamnionitis, endometritis, and surgical site infection. The current standard of care is not to treat women with asymptomatic BV in pregnancy.

Our objective is to conduct a double-blinded placebo controlled, pragmatic randomized controlled trial of metronidazole (500 mg twice daily for 1 week) versus standard of care (i.e., no antibiotics, receipt of placebo) to prevent peripartum infection (primary composite inclusive of chorioamnionitis, endometritis, and surgical site infection, SSI) among pregnant non-laboring women enrolled after 34 weeks of gestation.

1.2 specific aims:

Primary aim 1: To determine if administration of a 7 days course of metronidazole 500 twice daily versus placebo to women with BV, regardless of symptoms, diagnosed clinically after 34 weeks reduces the incidence of peripartum infection inclusive of chorioamnionitis, endometritis, and SSI.

Secondary aims:

Secondary aim 1: To evaluate whether BV treatment affects the frequency of peripartum infection based on BV gram stain results at the time of randomization and labor admission.

Secondary aim 2: To evaluate whether BV treatment affects the frequency of intrapartum and postpartum fever, and individual infectious morbidities, as well as neonatal complications, including neonatal sepsis and NICU admission.

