Neither the patient nor provider will be aware of treatment assignment. No significant adverse effects are expected with the use of antibiotics in the study population. As with any other instance in which antibiotics are administered, there is a chance of an allergic or other adverse reaction. The patient will receive standard inpatient monitoring during the labor course and in the postpartum period, and so any immediate adverse reaction can be promptly detected. The study period will be November 2020 to September 2022. The number of subjects studied will be 482 patients. If a patient wishes to withdraw from study after randomization and receipt of study medications, no additional interventions will be performed, but we will collect study outcomes as this is intent to treat study and patients' outcomes will be analyzed in the group they were assigned to.

5. INCLUSION CRITERIA:

- Pregnant women 18 to ≤50 years with the ability to give informed consent.
- Patients expected to have a vaginal delivery with no obstetric contraindication for vaginal delivery at time of screening.
- Gestational age ≥ 34 weeks

6. EXCLUSION CRITERIA:

- Plan for elective cesarean delivery
- Allergy or contraindications to metronidazole
- Receipt of metronidazole or clindamycin on admission for delivery for other indications.
- Hemodialysis
- Severe liver dysfunction
- Patient reports BV to nurse or clinician provider at current clinic visit or has been treated for BV within the past 3 months.

7. STUDY PROCEDURES:

7.1 Randomization and enrollment in clinic at or after 34 weeks: After obtaining informed consent, patients with a plan for vaginal delivery will be screened for BV by self-collecting 2 vaginal swabs for Gram stain, and Amsel criteria. A 3rd swab will be collected and stored at -80C for future microbiome analysis at the end of the study. The 3rd swab for future microbiome analysis is associated only with this study. When all study is complete, we will run the analysis to see if there is an association between microbiome and peripartum infections. The reason for storing the specimens and running them at the end is to decrease the cost. Patients with positive Amsel criteria will be eligible for randomization. Randomization and providing the patient with medications will be done at the same visit.

7.2 Clinical diagnosis of BV:

Amsel criteria are:

- Homogenous thin grayish-whitish discharge that coats vaginal mucosa
- Vaginal PH >4.5

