7.3 Confirmation of therapy success

Following completion of therapy, patients admitted to labor and delivery will have 1 additional swab. The swabs can be collected by the provider during performing normal labor exam or it can be self-collected by the patient. This swab will be sent to the lab for another gram stain. However, results will not be used for clinical decision guidance. It will be used for analysis later.

7.4 Clinical care: The care of patients in the remaining antepartum period, intrapartum period, including the method of induction or augmentation of labor will be according to standard of care at the participating site, and per the managing clinical team. After a subject who meets inclusion criteria agrees to participation in our study, the obstetric team will contact one of the investigators. Signed informed consent will be obtained by the PI, Co-Investigators or study coordinators. The total participation time in the study will be considered terminated at 6 weeks postpartum. No additional antepartum or postpartum will be required for the study, only routine visits will be recommended.

7.5 Data collection: The data collected will be kept on a password-secured Ohio State Wexner Medical Center (OSUWMC) computer. An encrypted USB flash drive will be used to transfer data. The data will be linked to the patient by patient's MRN number. This identifier is needed to access and analyze demographic data. During analysis of the data, all identifiers will be deleted.

7.6 Informed consent. Under the direction of the PI, trained research staff will be available 24/7 to screen and consent patients according to study protocol. Patients will be enrolled in clinic at or after 34 weeks gestation.

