
7.11. Study visits / Follow-up. Part of the standard of care, all postpartum patients are followed after delivery to assess any postpartum complications. Before the subject leaves the hospital, patients are usually given their follow up appointment. This will be documented in the datasheet, in order to ascertain follow up. Patients will be educated about the signs and symptoms of infection and other study outcomes and encouraged to call the study research team with any concerns. In addition, records of visits (to any hospital clinic or ER) prior to the routine postpartum visit will be obtained and reviewed to ascertain study outcomes (treating providers may also be called if clarifications are needed). Finally, if patient does not present to routine postpartum care, a research staff will call all patients at 6 weeks postpartum to inquire about occurrence of study outcomes. Newborn outcomes will be ascertained through initial discharge from hospital or up to 90 days or death, whichever occurs first. Readmissions and related diagnoses for infants will also be ascertained through medical records.

7.12. Withdrawals. Patients who withdraw from the study after randomization will be followed up to ascertain outcomes. Outcomes ascertained will be reported in intent to treat fashion.

7.13. Primary Outcome #1: Composite of chorioamnionitis, postpartum endometritis, SSI, wound infection, or other post Cesarean infections (occurring within 6 weeks after delivery) defined as follows. These outcomes will be defined and assessed by trained research staff and reviewed and validated by the investigators, all blinded to group assignment.

1) Chorioamnionitis: this will be diagnosed if patient develops: Fever (defined as either 2 readings of $\geq 38.0^{\circ}\text{C} / 100.4^{\circ}\text{F}$ 30 minutes apart or one reading $\geq 39.0^{\circ}\text{C} / 102.2^{\circ}\text{F}$) in the absence of any cause for fever PLUS one of the following: 1) fetal tachycardia (>160 for 30 minutes or longer), 2) Leukocytosis (> 15000 in absence of corticosteroids), 3) Purulent discharge from cervical os, 4) biochemical or microbiological changes of the amniotic fluid (positive gram stain, positive culture, low glucose, high WBC).(1)

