7.14 Secondary Outcomes

Maternal secondary outcomes:

- Individual infections: chorioamnionitis, endometritis, wound infection (including necrotizing fasciitis), other infections including abscess, septic thrombosis, pneumonia, pyelonephritis and breast infection
- Maternal Death
- Puerperal fever: Temperature > 100.4 F at least twice 30 minutes apart, or once with the use of antipyretic, or ≥ 101 F once. This will be analyzed for intrapartum and postpartum fever.
- Use of resources: Hospital stay, postpartum clinic or emergency room visit within 4 weeks of delivery, need for imaging or other invasive procedures, postpartum antibiotic use.
- Adverse events: Allergic reactions (anaphylaxis, angioedema, skin rashes including Stevens Johnson and Toxic Epidermal necrolysis), GI symptoms (nausea, vomiting, diarrhea, constipation, ileus, etc)

Neonatal secondary outcomes:

- Suspected sepsis (need for sepsis work-up): Presence of clinical signs/symptoms (hypothermia, fever, irritability, poor feeding, hypotonia, etc) causing the clinician to perform a sepsis work-up (blood, urine and/or cerebrospinal fluid, or chest X-ray), within 7 days of delivery- excludes routine work-up solely for positive maternal GBS status.
- Confirmed sepsis: Findings indicating positive cultures of blood, cerebrospinal fluid or urine obtained by catheterization or suprapubic aspiration, or cardiovascular collapse, or an unequivocal X-ray confirming infection in a clinically septic neonate, within 7 days of delivery.
- NICU admission and duration

- Neonatal morbidities:** Respiratory distress syndrome (RDS), necrotizing enterocolitis (NEC), periventricular leucomalacia (PVL), intraventricular hemorrhage (IVH), and BPD. RDS is presence of any one of i) oxygen requirement at 6-24 hours of life in a preterm infant, ii) abnormal chest radiograph consistent with RDS, or iii) need for surfactant; NEC is based on the clinical diagnosis of the neonatologist supported by findings on radiological imaging, surgical intervention and/or autopsy; IVH and PVL are diagnosed by an attending neonatologist based on clinical indications leading to a confirmatory ultrasound interpreted by a certified radiologist; BPD (or chronic lung disease) is defined as infant oxygen requirement at 28 days, at 36 weeks post-conceptual age or at time of hospital discharge

8. SOURCES OF RESEARCH MATERIAL: Electronic Medical chart/records.

9. POTENTIAL RISKS:

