Analysis will be performed by intent to treat. Univariable and multivariable analysis will be used to describe the population in the study and to identify potential confounding variable. For this analysis normality will be tested using Shapiro-Wilk method. Demographics and descriptive statistics such as t test, Pearson's chi-square, and Mann-Whitney tests will be used as indicated. Incidence rates between the study groups will be compared using Chi-square or Fisher Exact tests as appropriate. Data will be either shown as median [IQR], mean \pm SD, or n (%). Given this is a RCT, multivariate logistic regression may be used to adjust for confounding variables, should there be evidence of unbalanced distribution of these variables despite randomization

Sample size was calculated using a superiority trial design. The primary outcome will be the proportion of subjects having the composite infectious outcome. Clark et al evaluated 390 laboring patients and reported the incidence of chorioamnionitis and postpartum endometritis in patients with BV to be 16.4 % in contrast to 8.1 % among those without BV. This is an underestimate since it did not include the surgical site infections and other infectious morbidity in the composite primary outcome. Assuming the rate of composite infectious morbidities in women with BV to be at least 17% and estimating treatment effect to be 50%, we estimate that a sample size of 482 patients will need to be enrolled to have sufficient power of 80%, at an alpha 0.05. Given estimated incidence of BV, enrolling 1500 patients will be needed, given that only 30% will be randomized.

Rate in Placebo	Effect size	Number per group for power		
		80%	85%	90%
17%	50%	241	275	321

Secondary analysis: Given our estimated baseline composite primary outcome is about 10% regardless of BV, assuming that in patients with BV, the outcome might be higher up to 20%. Analysis will be performed to assess if a sample size of 398 patients (199 per group) will be sufficient to demonstrate a similar difference in primary outcome.

Sample size calculation using baselines primary outcome in our institution.

Rate in Placebo	Effect size	Number per group for power		
		80%	85%	90%
20%	50%	199	227	266

STATA 14 (College Station, TX) will be used for statistical analysis. This trial will be registered with Clinical Trials Register (Clinicaltrials.gov), before recruitment is initiated and after IRB approval.

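### The 36-week limb of the BPD definition falls at day 14 of life or earlier (or before birth) in infants born at or after 34 weeks, so early oxygen need in some late-preterm infants would be recorded as chronic lung disease

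*Combined protocol and SAP*

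**What the plan says.** Section 7.14 lists BPD among the neonatal morbidities, alongside RDS, NEC, PVL and IVH. Its wording begins "BPD (or chronic lung disease) is defined as" and continues "infant oxygen requirement at 28 days, at 36 weeks post-conceptual age or at time of hospital discharge". The three time points are alternatives. The text sets no minimum postnatal age, no range of gestational age at birth, and no requirement for a clinical diagnosis.

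The same list makes RDS positive on any one of three findings, the first being "oxygen requirement at 6-24 hours of life in a preterm infant".

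Entry is set by section 5 ("Gestational age ≥ 34 weeks") and section 7.6 ("Patients will be enrolled in clinic at or after 34 weeks gestation"). The abstract (1.1) describes the population as "pregnant non-laboring women enrolled after 34 weeks of gestation".

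On newborn follow-up, section 7.11 states: "Newborn outcomes will be ascertained through initial discharge from hospital or up to 90 days or death, whichever occurs first". It adds that infant readmissions and their diagnoses are taken from medical records.

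**The concern.** An oxygen requirement at 36 weeks indicates chronic disease only if the infant has by then been alive for some time. In this trial no infant can be born before 34 weeks, so the 36-week date comes soon after birth or has already gone by. The limb then picks up an infant still on oxygen for an early breathing problem, whereas the 28-day limb in the same sentence asks for persistence to four weeks.

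Two things are at stake. First, the reported BPD figure could include infants with short oxygen need, under a label that readers will take to mean chronic lung disease. Second, the outcome would not be the same for all infants: those born just before the 36-week date have three ways to qualify, and those born after it have two.

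Nothing else in the plan would catch this. In 7.14, NEC, IVH and PVL each rest on a neonatologist's diagnosis, but BPD rests on the time points alone. The investigator validation in 7.10 is specified for patients with the primary composite outcome, and no equivalent is stated for neonatal morbidities.

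**Working it through.** The plan gives no figure on this point to reproduce. The check is date arithmetic.

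**Inputs**
- Earliest birth: 34w0d = 34 × 7 = 238 days (sections 5 and 7.6; women are undelivered at entry).
- 36-week limb read as gestational age: 36 × 7 = 252 days.
- 36-week limb read literally from conception: 252 + 14 = 266 days. This assumes conception two weeks after the start of gestational dating; the documents do not define the term.

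**Formula:** day of life at the limb = 252 (or 266) − gestational age at birth in days. A negative result means that the date came before birth.

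| Birth | Days | Read as gestational age | Read from conception |
|---|---|---|---|
| 34w0d | 238 | day 14 | day 28 |
| 35w0d | 245 | day 7 | day 21 |
| 35w6d | 251 | day 1 | day 15 |
| 36w0d | 252 | day 0 | day 14 |
| 36w1d | 253 | 1 day before birth | day 13 |
| 37w0d | 259 | 7 days before birth | day 7 |
| 38w0d | 266 | 14 days before birth | day 0 |
| 39w0d | 273 | 21 days before birth | 7 days before birth |

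**Reading the table**
1. On the gestational-age reading, the limb can be applied only to births from 34w0d to 36w0d, at day 14 or earlier. That is at most half the age required by the 28-day limb (14/28).
2. On the literal reading, it can be applied to births from 34w0d to 38w0d. It matches the 28-day limb only at 34w0d and is earlier for every later birth.
3. On either reading, infants born after the cut-off can meet BPD only through the 28-day or discharge limbs.

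**The discharge limb.** It too has no minimum age. An infant sent home on oxygen in the first week meets BPD whatever the gestational age at birth. Removing the 36-week limb alone would therefore not make BPD rest on 28-day status.

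**Follow-up.** Section 7.11 ends routine ascertainment at the first of discharge, 90 days or death. For an infant discharged before day 28, oxygen status on day 28 is not directly observed. Readmission records need not show oxygen use at home.

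**The case against.** The strongest reply is that little depends on this. BPD is one item in a list of secondary morbidities. It is not in the primary composite (7.13) and does not enter the sample size (section 13). Secondary aim 2 and question 3.2.2 name neonatal sepsis and NICU admission, not BPD. Staff who abstract data are blinded (7.10), so misclassification should not by itself favour an arm. All of this stands, and it sets the severity.

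A reader might also infer more than the documents support:
- *That oxygen in the first days of life is generally recorded as BPD.* It is not. On the gestational-age reading only births from 34w0d to 36w0d are reached, and at 34w0d the time point is two weeks. Only births close to 36w0d are caught in the first days.
- *That the dividing line is 37 weeks.* That requires 36 weeks to mean the whole week up to 36w6d, which the text does not say. Under that reading the limb would extend to day 14 + 6 = 20 for a birth at 34w0d.
- *That a number of misclassified infants can be given.* It would need the distribution of gestational age at birth and the frequency of oxygen need at 36 weeks. The documents give neither.
- *That one oxygen episode is counted twice.* One episode in a preterm infant can meet both RDS and BPD, but they are listed as separate morbidities and no neonatal composite or event total is defined. The overlap makes the two outcomes harder to tell apart; it is not an analysis error.

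What the reply does not remove is that the rule, followed as written, gives the wrong label to some infants and is ambiguous about which ones.

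**Conclusion.** The point holds in a limited form, and it is minor. As written, early oxygen need in some late-preterm infants is recorded as BPD, and the definition differs by gestational age at birth. The affected births run from 34w0d to 36w0d (day 14 to day 0) if 36 weeks is gestational age, or from 34w0d to 38w0d (day 28 to day 0) if it is counted from conception. The number of infants cannot be stated.

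The conclusion rests on two things in the text: the limbs are alternatives with no minimum age, and all women are undelivered at 34 weeks or later. The second window also rests on the two-week assumption about conception. The consequence is confined to the reporting of one secondary neonatal outcome. The primary comparison and the sample size are unaffected, and with blinded abstraction bias between arms is unlikely.

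**What to change.** In 7.14 and on the neonatal data form:
1. Delete the 36-week limb from the BPD definition. This also removes the need to define post-conceptual age.
2. Apply the same 28-day minimum postnatal age to the discharge limb, so that an early discharge on oxygen is not BPD by itself.
3. State that, for infants discharged before day 28, the 28-day status is taken from oxygen status at discharge together with available records. Record it as unknown where these do not settle it, and report how many are unknown in each arm.

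The change should be made before neonatal outcomes are analysed. It costs a short edit to the definition and the form. The downside is a smaller BPD count and possibly some unknown 28-day statuses among infants who went home on oxygen, since 7.11 ends routine ascertainment at discharge for them.

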9.1. Randomization risk

Since antibiotics versus placebo will be randomized, it is possible that the patient may be in a group with higher adverse outcomes.

9.2. Loss of Confidentiality

Any time information is collected; there is a potential risk for loss of confidentiality. Every effort will be made to keep patient's information confidential; however, this cannot be guaranteed.

9.3 Risks from intervention

Most common adverse effects associated with metronidazole use are gastrointestinal, nausea, vomiting, anorexia, cramping, constipation and diarrhea, others adverse effects include headache. Metronidazole is categorized as pregnancy category B by FDA. GI adverse effects are common. Nausea affects about 12% of patients, diarrhea and abdominal pain affects 4%. Headache affects 18 % of patients. Hypersensitivity affects 5%. However, severe allergic reactions are very rare.

There are rare risks of serious peripheral and central nervous system issues, hematopoiesis, and cardiovascular and renal adverse reactions. Additionally, there are risks of drug interactions, including with alcohol. There are risk of fungal overgrowth/yeast infection and the risk of experiencing an unpleasant metallic taste. Metronidazole crosses the placental barrier. Though there is no evidence of harm to the fetus, it is present in breast milk for up to 24 hours after treatment ends.

10. SUBJECT SAFETY AND DATA MONITORING

The PI, Co-Investigators and study coordinators will be responsible for monitoring the safety of this study. The report will include participant demographics, expected versus actual recruitment rates, summary of any quality assurance or regulatory issues, summary of adverse events (AEs) or serious adverse events (SAEs) which may have occurred, and any changes in the protocol as a result of these issues.

The PI, Co-Investigators and study coordinators will ensure all aspects of data quality, including monitoring for adherence to consent procedures, inclusion and exclusion criteria, valid abstraction, correct entry, timeliness and responsiveness to data queries.

Data will be collected and stored with the participant ID code only. The master enrollment log linking patient identifiers with study ID numbers will be kept in a password-protected database

on the Ob/Gyn Department's internal server separate from the data. Several data collection forms will be used. Data on these forms devoid of personal identifiers will be securely stored at our perinatal research division. The research coordinator will be available to monitor the data and correct any discrepancies based on source documents if needed.

11. PROCEDURES TO MAINTAIN CONFIDENTIALITY:

- The data collected will be indirectly linked to the subject by patient's MRN number.
- When the subject accepts to participate in the study, a number will be attributed to the patient - from BVO1 to BVO482 - and this number will be entered on the data collection sheet.
- The data collected will be transferred to the PI's password-secured computer that is stored in a locked room using an USB flash drive.
- The study PI will be the only person to have a list with the number designated to each subject and the corresponding patient's MRN number. This list will be kept in a locked cabinet of the PI's locked office. This identifier is needed to access and analyze demographic data. During analysis of the data, all identifiers will be deleted.
- Data will not be disclosed to outside persons or entities.

12. POTENTIAL BENEFITS:

Subjects receiving the metronidazole may have a decreased risk of peripartum infection. If this is the case, our study stands to benefit women with BV who may undergo induction of labor or spontaneous labor in the future.

13. STATISTICAL APPROACH:

Analysis will be performed by intent to treat. Univariable and multivariable analysis will be used to describe the population in the study and to identify potential confounding variable. For this analysis normality will be tested using Shapiro-Wilk method. Demographics and descriptive statistics such as t test, Pearson's chi-square, and Mann-Whitney tests will be used as indicated. Incidence rates between the study groups will be compared using Chi-square or Fisher Exact tests as appropriate. Data will be either shown as median [IQR], mean \pm SD, or n (%). Given this is a RCT, multivariate logistic regression may be used to adjust for confounding variables, should there be evidence of unbalanced distribution of these variables despite randomization

Sample size was calculated using a superiority trial design. The primary outcome will be the proportion of subjects having the composite infectious outcome. Clark et al evaluated 390 laboring patients and reported the incidence of chorioamnionitis and postpartum endometritis in patients with BV to be 16.4 % in contrast to 8.1 % among those without BV. This is an underestimate since it did not include the surgical site infections and other infectious morbidity in the composite primary outcome. Assuming the rate of composite infectious morbidities in women with BV to be at least 17% and estimating treatment effect to be 50%, we estimate that a sample size of 482 patients will need to be enrolled to have sufficient power of 80%, at an alpha 0.05. Given estimated incidence of BV, enrolling 1500 patients will be needed, given that only 30% will be randomized.

Rate in Placebo	Effect size	Number per group for power		
		80%	85%	90%
17%	50%	241	275	321

Secondary analysis: Given our estimated baseline composite primary outcome is about 10% regardless of BV, assuming that in patients with BV, the outcome might be higher up to 20%. Analysis will be performed to assess if a sample size of 398 patients (199 per group) will be sufficient to demonstrate a similar difference in primary outcome.

Sample size calculation using baselines primary outcome in our institution.

Rate in Placebo	Effect size	Number per group for power		
		80%	85%	90%
20%	50%	199	227	266

STATA 14 (College Station, TX) will be used for statistical analysis. This trial will be registered with Clinical Trials Register (Clinicaltrials.gov), before recruitment is initiated and after IRB approval.

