3.2 Secondary Research Questions

3.2.1: Does treatment of BV with 7-day course of metronidazole >34 weeks decrease the incidence of Gram stain +ve for BV at time of admission for labor?

[figure not shown]
Hypothesis : Treatment of BV will reduce the incidence of +ve Gram stain for BV at time of admission for labor.

3.2.2: Does treatment of BV with 7-day course of metronidazole >34 weeks decrease the incidence of neonatal complications including neonatal sepsis and NICU admission?

Hypothesis : Treatment of BV will reduce the incidence of neonatal complications.

3.2.3: Hypothesis : Does treatment of BV decrease utilization of health care services including maternal ER visits, postpartum clinic visits, OB triage visits, and postpartum hospital readmissions?

Hypothesis: Treatment of BV will reduce health care services utilization

4. STUDY DESIGN:

4.1 Study enrollment: We propose a double-blinded, placebo controlled, multi-center randomized trial of 482 pregnant women who are diagnosed with BV in late 3rd trimester (>34 weeks). During routine clinic visit after 34 weeks, prospective patients will be counseled about the study. Patients who agree to be enrolled, will sign informed consent.

Following enrollment, patients will be screened for BV. Those patients who are BV positive, will be randomized to receive either metronidazole 500 mg BID orally for 7 days or identically appearing placebo. The PI, Co-Investigators or study coordinators will be responsible for the informed consent.

1500 participants will be enrolled for screening to randomize 482 participants.

4.2 Study sites: This will be a multi-center, double-blinded randomized clinical trial. The primary site will be OSUWMC. The secondary center will be University of Texas Medical Branch, Galveston, Texas, and may include additional medical centers over time. The study period will be between November 2020 to September 2022. The number of subjects studied will be 482 patients. If a patient wishes to withdraw from study after randomization and receipt of study medications, no additional interventions will be performed, but we will collect study outcomes with patient consent as this is intent to treat study and patients' outcomes will be analyzed in the group they were assigned to.

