7.8 Randomization and Masking: After obtaining informed consent, women with BV will be randomized to either control or study group according to a randomization sequence that is computer generated and maintained by the investigational drug pharmacy. A study enrollment log with a study ID number, subject name and medical record number, will be used to track enrolled patients. The investigational pharmacy at OSUMC will be notified after randomization and study drugs or placebos will be sent as dictated by patient's randomization group.

7.9 Drug Administration and Dispensation. Once a subject is consented randomization will be performed by the OSUWMC's investigational drug pharmacy (IDS). The appropriate study drug according to the group assignment will then be dispensed by OSUWMC's investigational drug services (IDS) pharmacy as well. Patients will receive 7 days of metronidazole 500 BID oral or similarly appearing placebo. The 14 pills will be provided in a container. The IDS pharmacy will dispense the drugs, account for dispensing and stock number. Funding provided by the department will cover the cost of the medications, and the patient's insurance company will not be billed. Subjects will be instructed to bring the container to clinic next visit or on admission to labor and delivery to count remaining pills and assess adherence.

The subject will be included in the analysis by intent-to-treat.

7.10 Baseline Procedures. Routine Ante, intra- and postpartum care will be provided to patients according to the local standard of care. Patients' clinical providers who will be blinded to the study interventions. Trained and experienced research staff (also blinded to group assignment) will be responsible for screening patients in clinic for eligibility and for all research data abstraction. All data will be de-identified after collection and tracked only with a study ID number.

The PI and co-PI will review and validate the diagnosis for all patients identified to have the primary composite outcome, applying current CDC and other standard criteria. These reviews

will be conducted masked to treatment group. If there is uncertainty, a second investigator will review the chart, discuss with the PI as needed, and make a final determination regarding the outcome. Maternal and neonatal outcomes will be assessed in the hospital following delivery (on an ongoing basis until discharge) and at the routinely scheduled postpartum follow-up visits up to 6 weeks postpartum.

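### Does the sentence about 398 patients commit the trial to a second test, or an early stop, short of its target of 482?

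*Combined protocol and SAP*

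**What the plan says.** Section 13 (Statistical Approach) opens its sizing in the past tense: "Sample size was calculated using a superiority trial design". It takes a composite infection rate of at least 17% on placebo and a 50% treatment effect, and concludes: "we estimate that a sample size of 482 patients will need to be enrolled to have sufficient power of 80%, at an alpha 0.05". A small table gives 241, 275 and 321 per group for 80%, 85% and 90% power.

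A paragraph labelled *Secondary analysis* follows. It puts the institution's composite rate at about 10% regardless of BV, supposes that it may be as high as 20% in women with BV, and states: "Analysis will be performed to assess if a sample size of 398 patients (199 per group) will be sufficient to demonstrate a similar difference" in the primary outcome. Directly beneath is a second table with the same columns, captioned "Sample size calculation using baselines primary outcome in our institution". It gives 199, 227 and 266 per group for a 20% placebo rate and the same 50% effect.

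Elsewhere the target does not vary. Section 4.1 says "1500 participants will be enrolled for screening to randomize 482 participants". Section 4.2 says "The number of subjects studied will be 482 patients". Section 11 numbers participants up to 482, and Section 14 builds feasibility on 482. On blinding, Section 4.2 says "Neither the patient nor provider will be aware of treatment assignment", and Section 7.10 says that outcome reviews "will be conducted masked to treatment group". Section 7.8 leaves the randomization sequence with the investigational pharmacy.

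**The concern.** Three features of the 398 sentence make it look like more than a planning note. Its label is that of an analysis. It is in the future tense, although the calculation it seems to refer to is printed just below. And its object is the primary outcome. Section 13 names the test for the composite (chi-square or Fisher exact) but does not say when, or how many times, it is applied.

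If the sentence really meant an outcome look after 398 women, two things would be at stake. Testing the arms at 0.05 at both 398 and 482, with either result accepted as success, would push the type I error above the stated 0.05. Ending enrolment at 398 would lower power below 80% at the plan's own base-case rate of 17%.

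**Working it through.** **Inputs, all from Section 13.** Placebo rates 17% and 20%; effect 50%, so treated rates 8.5% and 10%; alpha 0.05; power 80%; 241 or 199 per group. Equal allocation is implied by the per-group figures. The sidedness of alpha is not stated and is inferred in step 1.

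**1. Reproduce the plan's figures.** With pooled variance under the null and p̄ the mean of the two rates,

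n per group = [1.960·√(2p̄(1−p̄)) + 0.8416·√(p₁(1−p₁)+p₂(1−p₂))]² / (p₁−p₂)².

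- 17% against 8.5%: p̄ = 0.1275. The terms are 1.960 × 0.4717 = 0.9245 and 0.8416 × 0.4678 = 0.3937. Their sum is 1.3182, its square 1.7377, and 1.7377/0.007225 = 240.5, so 241 per group and 482 in total.
- 20% against 10%: p̄ = 0.15. The terms are 1.960 × 0.5050 = 0.9897 and 0.8416 × 0.5000 = 0.4208. Their sum is 1.4105, its square 1.9896, and 1.9896/0.01 = 199.0, so 199 per group and 398 in total.

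The other four table entries agree to within one patient (322 against the printed 321, 228 against the printed 227, and 275 and 266 exactly). A one-sided 0.05 would give 190 and 157, so the plan's alpha is two-sided. Both tables therefore come from one formula, and the second is a completed power calculation with a different placebo rate.

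**2. Power at each size.** Power = Φ{[(p₁−p₂)√n − 1.960·√(2p̄(1−p̄))] / √(p₁(1−p₁)+p₂(1−p₂))}.

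| Per group | 17% vs 8.5% | 20% vs 10% |
|---|---|---|
| 199 | (1.1991 − 0.9245)/0.4678 = 0.587, power 72.1% | (1.4107 − 0.9897)/0.5 = 0.842, power 80.0% |
| 241 | (1.3196 − 0.9245)/0.4678 = 0.844, power 80.1% | (1.5524 − 0.9897)/0.5 = 1.125, power 87.0% |

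Keeping 482 costs no power if the rate is really 20%. Only a stop at 398 would cost power, and only if the rate is below 20%.

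**3. Type I error if a test at 398 were added.** The two test statistics have correlation √(398/482) = 0.909. The chance under the null that either exceeds 1.960 in absolute value is about 0.069. If the 398 result carried no claim, the test at 482 would keep its 0.05.

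**4. Which reading the text supports.** Whether a sample size is sufficient depends on the assumed rates and effect. It is a power question, and comparing the arms after 398 women would not answer it. The sentence stands between the assumption that answers it (up to 20%) and the table that gives the answer (199 per group). The document mentions no interim look, no decision attached to 398 and no division of alpha. The monitoring report in Section 10 lists demographics, recruitment, quality and regulatory issues, adverse events and protocol changes, with no comparison of outcomes.

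**The case for a change.** The strongest case for a change is that a stated target and masked staff do not fix how often the primary outcome is tested. The calculation at 199 per group is already printed, so an analysis still to come must, on a literal view, be something else. Nothing says in words that the composite is tested once, or what happens if 398 is found sufficient. One sentence would settle it, and it is most credible when written before outcomes are known.

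Part of this stands. The label and the tense are poorly chosen, and the single test is left to be understood. But a plan that describes no interim analysis is ordinarily read as having one final analysis, and silence does not authorise another. Each harmful outcome needs steps the document does not contain. The inflated error needs an arm comparison at 398, at an unadjusted 0.05, with either result counting. The lost power needs a decision to stop at 398. Against that stand the caption, the matching tables and a target of 482 in every operative section. Adding the sentence would tidy the text without altering the sample size, the test, the alpha or any result.

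**Conclusion.** The concern does not call for a change. The 398 figure is almost certainly an alternative planning scenario (20% against 10%) written in the wrong tense under an awkward label. Followed in the ordinary way, the plan compares the composite once, at 482, with two-sided type I error 0.05 and power 80.1% at 17% against 8.5%, which is what it states. If the true placebo rate is 20%, power at 482 is 87.0%.

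The 6.9% error and the 72.1% power describe departures that the plan does not prescribe. The conclusion rests on two assumptions: that the 398 sentence belongs to the table it introduces, and that the absence of any interim procedure means none is intended. If the sponsor did mean to look at outcomes by arm at 398, or to stop there, that would be a new design element needing its own specification, and this conclusion would not cover it.
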